6.3.1.2. Analysis of secondary endpoints

The following secondary endpoints will be analyzed:

- KOOS score at 12 months after surgery
- relative GAG-content (rel. $\Delta R1$) by delayed gadolinium-enhanced MRI of cartilage (dGEMRIC) 3, 12 and 24 months after surgery
- MOCART score at 3, 12 and 24 months after surgery
- EQ-5d score at 12 and 24 months after surgery

All secondary endpoints will be analyzed with a linear mixed effects model as described for the sensitivity analysis of the primary endpoint (with the corresponding baseline scores as covariate). If necessary, endpoints will be transformed in order to fulfill assumption of a normal residual distribution, or, if no reasonable transformation can be found, generalized linear mixed-effects models will be applied.

6.4. Missing data

The number of non-missing observations will be presented for each endpoint. We will use multiple imputations in case primary outcome assessments are missing, based on baseline and outcome variables (see next paragraph). Since missing values in these variables are possible, chained equations will be used. Continuous variables will be imputed using linear regression and binary variables using logistic regression. We will construct and analyse 20 imputed data sets and combine results using Rubin's rules.³

Baseline patient characteristics and outcome variables (e.g. KOOS sub-scores) will be considered for multiple imputations. Variables with more than 50% missing values will not be used for the imputation model. Categorical variables with a frequency of 5% or less in one category will also be omitted. If two binary variables accord in more than 95% or less than 5% of patients, only one will be used.

6.5. Evaluation of safety parameters

Evaluation of safety parameters will be based on the safety population (FAS, section 4.4). They will be listed according to the treatment the patient actually received with the time points of onset. If many adverse events should be observed, we will compare frequency between treatment groups.

6.6. Statistical software

The statistical analysis will be performed by Surgical Outcome Research Center using the statistical software Stata 16.0 (StataCorp LLC, 4905 Lakeway Drive, College Station, Texas 77845).

7. Changes from the Study Protocol

7.1. Analysis set

Two randomized patients did not receive treatment and study outcome (KOOS score at 24 months after surgery) was not assessed in these patients. So conducting the analysis according to ITT was not possible. We hence analysed the PPS instead of the FAS.

7.2. Further secondary outcomes

As further secondary outcomes, we included all 5 KOOS sub-scores (symptoms, pain, activity of daily living, sport and quality of life) assessed at 12 and 24 months postoperatively. Indeed these sub-scores typically provide important information with respect a patients' benefit from either treatment.

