11.4.3 Secondary Analyses

The following secondary endpoints will be analyzed:

- KOOS score at 12 months after surgery
- relative GAG-content (rel. □R1) by delayed gadolinium-enhanced MRI of cartilage (dGEMRIC) 3, 12 and 24 months after surgery
- MOCART score at 3,12 and 24 months after surgery
- EQ-5d score at 12 and 24 months after surgery

All secondary endpoints will be analyzed with a linear mixed effects model as described for the sensitivity analysis of the primary endpoint (with the corresponding baseline scores as covariate). If necessary, endpoints will be transformed in order to fulfill assumption of a normal residual distribution, or, if no reasonable transformation can be found, generalized linear mixed-effects models will be applied.

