2.4. Framework

All endpoints will be analysed for the superiority of N-TEC compared to N-CAM.

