4.2. Confidence intervals and p-values

The statistical testing will be two-sided with a significance level of 5%. All tests will be accompanied by an effect measure (N-TEC vs N-CAM) with a 95% confidence interval (95% CI).

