7.3. Sensitivity analysis

We found that the distribution of KOOS at the time of outcome had the pattern of a ceiling effect in both treatment arms (Fig 1), even more pointed in the N-TEC group. Thus, the median (solid line) is a better summary measure than the mean (dashed line).

Figure 1. Distribution of primary outcome

[figure not shown]

Figure 1. Distribution of primary outcome

Hence, we decided to use median regression models to derive treatment effect with standard errors (SE) estimated based on bootstrapping with 5000 repetitions. We chose bootstrapped SEs to avoid 95% CIs exceeding 100, since there are no data points over 100 to bootstrap from. We furthermore adjusted for baseline KOOS score to gain precision of the treatment effect, given that the outcome is derived from self-ratings and dropped center as random effect.

8. References

2. <http://www.consort-statement.org/consort-2010>
3. Rubin DB. Multiple **imputation for nonresponse** in surveys. New York: John Wiley & Sons; 2004.

[name], the 28th of November 2022

A handwritten signature in blue ink that reads "[name]".

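### SAP 7.2 adds ten KOOS sub-score comparisons as secondary outcomes, in a section written after overall KOOS had been viewed by arm, and does not mark them as exploratory

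*SAP*

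**What the plan says.** Protocol 11.4.3 introduces its list with "The following secondary endpoints will be analyzed" and names overall KOOS at 12 months, dGEMRIC and MOCART at three visits each, and EQ-5d at two visits. SAP 6.3.1.2 repeats that list. Neither contains a between-arm comparison of a KOOS sub-score.

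SAP section 7 sets out changes from the protocol. In 7.2 it says: "As further secondary outcomes, we included all 5 KOOS sub-scores", at 12 and at 24 months. The reason given is general: sub-scores tell the reader something about patient benefit. No decision date is given.

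In the next subsection, 7.3, the SAP reports on the primary outcome: "We found that the distribution of KOOS at the time of outcome had the pattern of a ceiling effect in both treatment arms", and adds that it was "even more pointed in the N-TEC group". SAP 6.2 defines that primary outcome as the mean of the five sub-scores.

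On inference, SAP 2.4 says "All endpoints will be analysed for the superiority of N-TEC compared to N-CAM", and SAP 4.2 says "The statistical testing will be two-sided with a significance level of 5"%. There is no hierarchy or multiplicity rule, and no endpoint is set apart as exploratory.

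**The concern.** A reader of the final report will find the ten sub-score results beside the planned secondary endpoints, with the same label and the same test. The two groups do not have the same standing. The planned endpoints were fixed in the protocol. The sub-scores are first listed for between-arm comparison in text that, as it stands, was written with by-arm outcome data in view. The 24-month data that had been viewed are not separate from the added outcomes, because the sub-scores are the components of the viewed score.

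The practical risk is this. If overall KOOS misses significance, one favourable sub-score could be reported as a secondary superiority result. KOOS is self-rated, and Protocol 6.1 and 6.2.2 say that patients can tell which graft they received. That makes an unplanned sub-score finding weaker still as a basis for a claim.

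**Working it through.** The documents give no error rate for the secondary outcomes, so there is no plan figure to reproduce on this point itself. The plan's only design calculation concerns the primary endpoint, and it does reproduce:

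- Inputs from Protocol 11.2 and SAP 2.3: means 75 and 85, SD 17, values capped at 100, two-sided 5% t-test.
- Simulation (20,000 runs per size) gives power of 79.9% at 96 patients and 80.2% at 98, in line with 97 evaluable at 80%.
- Drop-out of 10%: 97 / 0.90 = 107.8, rounded up to 108.

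This calculation covers overall KOOS only. No sub-score enters it, so relabelling the sub-scores changes nothing in it.

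**What was added.** 5 sub-scores × 2 visits = 10 comparisons. The planned list holds 1 (KOOS at 12 months) + 3 (dGEMRIC) + 3 (MOCART) + 2 (EQ-5d) = 9, with no sub-score among them.

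**Timing.** Three facts bear on when section 7 was written.

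- SAP 7.1 says in the past tense that the per-protocol set was analysed.
- SAP 7.3 describes the 24-month overall KOOS in each arm.
- The SAP is dated 28 November 2022, and the protocol synopsis planned the last 24-month visit for October 2021, 13 months earlier.

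Together they show that the section in its present form postdates by-arm inspection of overall KOOS. They do not date the decision in 7.2. They also do not show that any sub-score result, or any 12-month result, had been seen by arm.

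**Status.** SAP 2.4 covers every endpoint, and 4.2 sets the level. Nothing in 7.2 exempts the additions, so they fall under both.

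**Error rate of ten unadjusted tests (context only).**

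- Independent, either direction: 1 − 0.95^10 = 1 − 0.599 = 0.401, or 40%.
- Independent, in favour of N-TEC only: 1 − 0.975^10 = 1 − 0.776 = 0.224, or 22%.
- Correlated: ten normal test statistics, with correlation ρ between sub-scores and r between visits, combined as a Kronecker product; 400,000 runs per setting. Both correlations are assumptions, since the documents give none.

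| ρ | r | Either direction | Favouring N-TEC |
|---|---|---|---|
| 0.5 | 0.5 | 31.1% | 15.8% |
| 0.7 | 0.5 | 25.6% | 12.7% |
| 0.7 | 0.7 | 23.6% | 11.8% |
| 0.9 | 0.7 | 16.3% | 8.2% |

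**The case against.** The other side has several good arguments.

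- **Disclosure.** The addition sits openly under changes from the protocol, with a reason. Protocol 11.4.6 asks for deviations to be listed and justified. This stands: nothing is hidden. But disclosure tells the reader that the outcomes are new, not how much weight they can bear.
- **No selection.** All five sub-scores were added, at both post-baseline questionnaire visits. A reader might infer that sub-scores were picked because they looked favourable. The documents do not support that: the set is complete, the stated reason is general, and no sub-score result is described.
- **Not wholly new.** Protocol 9.2.4 already planned to analyse deterioration on KOOS and its five sub-scores. This stands in part. It shows that the sub-scores were planned study measures, but it concerns deterioration and does not specify between-arm comparisons at 12 and 24 months.
- **No confirmatory claim.** A reader might infer that 7.2 gives the sub-scores confirmatory status. No text calls any secondary outcome confirmatory, and only the primary endpoint is powered. The supportable point is narrower: the additions share the label and framework of the planned secondary endpoints.
- **The error rates measure multiplicity, not post hoc choice.** This is correct. Ten tests written into the protocol at the outset would give the same 40%, and independence is implausible for five domains of one questionnaire in the same patients. The planned secondary endpoints have no multiplicity procedure either.

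**Conclusion.** The point holds as one of status and timing. Ten comparisons outside both secondary analysis lists were added in a section written, as it stands, after overall KOOS had been viewed by arm. The SAP does not show that the decision came first, and it leaves the ten under the superiority framework that governs the planned secondary endpoints.

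The conclusion rests on the wording of the documents and needs no assumption about correlations. The error rates only illustrate what ten unadjusted tests can produce. Under the assumed correlations (0.5 to 0.9 between sub-scores, 0.5 to 0.7 between visits), a false finding in favour of N-TEC has a probability of about 8% to 16%, against 2.5% for a single test. The 40% should not be read as the effect of adding outcomes late.

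**What to change.** In SAP 7.2:

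- label the ten sub-score comparisons as post hoc and exploratory;
- exempt them explicitly from the superiority framework in 2.4;
- report each as an estimate with a 95% interval and no superiority claim;
- state when they were added relative to first access to outcome data by arm.

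The secondary lists in Protocol 11.4.3 and SAP 6.3.1.2 stay as they are.

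The cost is a change of wording and the loss of superiority claims on single sub-scores. No data are withheld, since all ten estimates are still reported.

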7.3. Sensitivity analysis

We found that the distribution of KOOS at the time of outcome had the pattern of a ceiling effect in both treatment arms (Fig 1), even more pointed in the N-TEC group. Thus, the median (solid line) is a better summary measure than the mean (dashed line).

Figure 1. Distribution of primary outcome

[figure not shown]

Figure 1. Distribution of primary outcome

Hence, we decided to use median regression models to derive treatment effect with standard errors (SE) estimated based on bootstrapping with 5000 repetitions. We chose bootstrapped SEs to avoid 95% CIs exceeding 100, since there are no data points over 100 to bootstrap from. We furthermore adjusted for baseline KOOS score to gain precision of the treatment effect, given that the outcome is derived from self-ratings and dropped center as random effect.

8. References

2. <http://www.consort-statement.org/consort-2010>
3. Rubin DB. Multiple **imputation for nonresponse** in surveys. New York: John Wiley & Sons; 2004.

[name], the 28th of November 2022

A handwritten signature in blue ink that reads "[name]".

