Number of Participants with Rationale:	The total number of Patients is 108 trial participants considering an overall drop-out rate of 10%. Each group will consist of 54 patients. The patients will be recruited and treated by five centers in Switzerland, Germany, Croatia and Italy to achieve a defined number of patients per center. This sample size is estimated to be able to show the superiority of N-TEC to N-CAM regarding the primary endpoint and is based on the study of Saris et al., 2008.
Study Duration:	Estimated duration is 4 years for the main investigational plan (i.e. from start of screening of first participant to last participant processed and finishing the study)
Study Schedule:	01/2017: Treatment of first patient
	10/2019: Treatment of last patient
	01/2019: 24 months (final) follow-up of first patient
	10/2021: 24 months (final) follow-up of last patient

Document:	Clinical Study Protocol
Version:	V07
Page number:	15 of 80
Acronym	Nose to Knee II

Investigator(s):

Sponsor Investigator / Principal Investigator (CH)

[name]. med. [name]

Department of Traumatology, University Hospital Basel,

[name]

[contact] [contact]

email: [contact]

Principal Investigator / study coordinator (CH)

[name]

Department of Traumatology, University Hospital Basel.

[name]

[contact] [contact]

email: [contact]

Principal Investigator (D)

[name]

Medical Center - University of Freiburg, Germany

Department of Orthopedics and Trauma Surgery [name]

[contact] [contact]

Email: [contact]

Principal Investigator (HR)

[name]. [name]

Department of Orthopaedic Surgery, University Hospital Sveti Duh,

[name]

[contact]

Email: [contact]

Principal Investigator (I)

[name]. [name]

Istituto Ortopedico Galeazzi (IOG) [name]

[contact] Email: [contact]

Principal Investigator (D)

[name]

Orthopedic Clinic König-Ludwig-Haus

Lehrstuhl für Orthopädie der Universität Würzburg [name]

[contact] [contact]

Email: [contact]

Study Protocol Nose to Khee II, April 10, 2018, Version 07

Page 15 of 80

Document:	Clinical Study Protocol
Version:	V07
Page number:	16 of 80
Acronym	Nose to Knee II

Other investigators	[name] [name] (CH)
	PD [name] (D)
	[name] (HR)
	[name] (I)
	[name] (D)
Study Centre(s):	5 Centers:

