6.3. Analysis methods

6.3.1 Primary analysis

The primary analysis will be done on the PPS. Missing data will be handled according to section 6.4. Primary objective is to demonstrate in patients younger than 65 years with articular knee

cartilage injuries the superiority of N-TEC to N-CAM, assessing by KOOS measured 24 months after surgery.

The primary endpoint will be analyzed with a linear mixed effects model, including therapy (N-TEC vs. N-CAM; categorical variable) as single explanatory variable (fixed effect), and including study center as random effect variable to account for the multicenter study design.

As a sensitivity analysis, we will analyze the primary endpoint by adjusting for covariates and testing for interactions. The linear mixed-effects model will include therapy (N-TEC vs. N-CAM; categorical variable), onset of symptoms (stratified categorical: acute: ≤ 1 years; chronic: > 1 years) and the covariate baseline KOOS (continuous variable) as explanatory variables (fixed effects). In addition, the model will include the interaction between therapy and onset of symptoms. A significant interaction would indicate that the outcome of the therapy depends on how long the symptoms have been present. Further, study center will be included as a random effect variable in the model to account for the multicenter study design.

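### SAP 7.3 adds a median regression chosen after the 24-month KOOS was seen by arm; its role beside the 6.3.1 models, the dropped centre effect and the stated reason for its intervals need correcting

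*SAP*

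**What the plan says.** SAP 6.3.1 (Primary analysis) keeps the model of Protocol 11.4.2: a linear mixed model for KOOS at 24 months with therapy as the only fixed effect and centre as a random effect. The analysis set was changed there ("The primary analysis will be done on the PPS"), but the model was not. The same section plans a sensitivity model that adds symptom onset, its interaction with therapy, and baseline KOOS, and again keeps centre. SAP 2.2 makes centre the stratification factor of the randomisation.

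SAP 7.3 is headed as a sensitivity analysis and stands in section 7, the chapter on changes from the protocol. It says that the 24-month KOOS "had the pattern of a ceiling effect in both treatment arms (Fig 1), even more pointed in the N-TEC group", and continues: "Thus, the median (solid line) is a better summary measure than the mean (dashed line". Then: "Hence, we decided to use median regression models to derive treatment effect with standard errors (SE) estimated based on bootstrapping with 5000 repetitions". On the intervals: "We chose bootstrapped SEs to avoid 95% CIs exceeding 100, since there are no data points over 100 to bootstrap from". The last sentence adds adjustment for baseline KOOS to gain precision, "given that the outcome is derived from self-ratings and dropped center as random effect".

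The SAP is dated "the 28th of November 2022". The study schedule in the protocol synopsis has "10/2021: 24 months (final) follow-up of last patient".

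**The concern.** A summary measure and model chosen after the outcome has been seen by arm cannot carry the same weight as one fixed beforehand. That does no harm if the reader is told plainly that the analysis is post hoc and supportive. SAP 7.3 leaves this to inference. Its heading says one thing; its statement that the median is the better measure, and its use of the median regression to obtain the treatment effect, say another. It also leaves open whether the sensitivity model of 6.3.1 will still be reported.

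Two technical points follow. Leaving out the randomisation stratifier needs a reason, and none is clearly given. The reason for bootstrapped standard errors does not hold for the intervals described. At stake are what may be concluded from the median result, some power, and the correctness of a methods statement.

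**Working it through.** **1. Order of events and role.** The post hoc status follows from the wording of 7.3: a pattern was found in both arms and the model was then decided on. The dates agree with this (SAP November 2022, planned last visit October 2021) but are not needed for it. SAP 7.1 says explicitly that one analysis set was used instead of another. SAP 7.3 has no such wording, neither instead of nor in addition to.

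**2. The plan's own figure.** Inputs (SAP 2.3): N(75, 17) against N(75 + 10, 17), values above 100 set to 100, two-sided t-test at 5%, 97 evaluable.
- Without the cap: n per arm = 2 × (1.96 + 0.84)² × 17² / 10² ≈ 45.3, so 46 per arm and 92 in total; power at 97 is 82.6%.
- With the cap, by simulation (40,000 trials): 80.5% at 97. The stated 80% reproduces.
- Dropout: 97 / 0.90 = 107.8, so 108.

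The plan therefore already allowed for a ceiling and still compared means.

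**3. Free choice between two analyses.** Further assumptions, since the documents give none: centres of 20/20/19/19/19, a normal baseline, and the correlations and centre SDs below (total SD held at 17). There were 3,000 null trials per setting, with Monte Carlo SE about 0.5 points. The median regression used 150 bootstrap draws (the SAP has 5000) and an approximate fit; against an exact fit on 30 data sets, coefficients differed by 0.07 points at the median and 0.9 at most.

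| Null, centre SD 0 | r = 0 | 0.3 | 0.5 | 0.7 |
|---|---|---|---|---|
| Mixed model of 6.3.1 | 5.3% | 5.1% | 5.6% | 5.0% |
| Median regression of 7.3 | 4.2% | 4.8% | 5.0% | 3.8% |
| Either significant | 7.5% | 8.1% | 8.6% | 7.6% |
| Either, favouring N-TEC (nominal 2.5%) | 3.8% | 4.1% | 3.9% | 4.0% |

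At r = 0.5 with centre SD 5 and 8, either is significant in 8.0% and 6.0%. An unadjusted version (difference in medians against t-test) gave 6.9%. For comparison, free choice between an unadjusted and a baseline-adjusted comparison of means, simplified to leave out centre, onset and the interaction, gave 6.6%, 7.6% and 8.0% at r = 0.3, 0.5 and 0.7.

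**4. Centre.** Same set-up, r = 0.5; power at a shift of 10 from 2,000 trials each (SE about 1 point).

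| Median regression | SD 0 | SD 5 | SD 8 |
|---|---|---|---|
| Type I error, no centre | 5.0% | 4.1% | 2.7% |
| Type I error, centre fixed, resampling within centre | 4.1% | 4.1% | 3.0% |
| Power, no centre | 71.6% | 72.3% | 70.2% |
| Power, centre fixed, resampling within centre | 70.9% | 74.7% | 78.8% |

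Power lost by omission: 70.9 − 71.6 = −0.7 (within simulation error), 74.7 − 72.3 = 2.4, and 78.8 − 70.2 = 8.6 points.

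**5. Intervals.** A limit built from a standard error is estimate + 1.96 × SE. That no resampled value exceeds 100 bounds the resampled medians, not this sum. For an arm median M the limit passes 100 whenever SE > (100 − M) / 1.96:
- M = 85: 15 / 1.96 = 7.65
- M = 90: 10 / 1.96 = 5.10
- M = 95: 5 / 1.96 = 2.55

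The large-sample SE of a median at n = 49 and SD 17, ignoring the cap, is 1.253 × 17 / 7 = 3.04, so M = 95 is clearly exposed. In simulation (6,000 trials) the limit passed 100 in 0.8%, 12.7% and 59.9% of trials at latent means 85 (planned), 90 and 95 (assumed). Percentile limits never did.

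SAP 4.2 attaches the interval to the N-TEC versus N-CAM effect. A difference between two scores on 0 to 100 lies between −100 and 100, so the ceiling of the score does not bear on it. The largest upper limit for the between-arm median effect in 28,000 simulated trials was 41.5.

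**The case against.** The other side has a good case. The heading calls 7.3 a sensitivity analysis. When the authors changed the primary analysis set they edited 6.3.1 and left the model alone, so the mixed model is naturally still primary. The order of events is disclosed, in the chapter on changes; only the label is missing. Standard median regression has no random-intercept term, so losing centre as a random effect may simply follow from the model class. The remark that there is nothing above 100 to resample is the logic of percentile limits, so the interval sentence may be loose wording.

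Much of this stands, and it rules out several stronger readings that a reader might infer:
- *The median regression has replaced the primary model.* The heading and the retained 6.3.1 model speak against it.
- *The trial's type I error is 6 to 9%.* That holds only if either result may become the headline, and choice between two mean models gives nearly the same rate. It is not an effect of 7.3 in particular.
- *Protocol 11.4.6 has been breached.* Its duty to list and justify deviations is to be met in a chapter of the final statistical report, which is not among these documents.
- *The 10-point value has become ambiguous.* SAP 2.3 simulates it as a shift in the mean of the underlying normal distribution, tested by a t-test, and declares superiority on significance, not on an estimate reaching 10.
- *Leaving out centre inflates false positives.* In these simulations it did not.

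What the objection does not answer is the missing statement of role, especially towards the planned sensitivity model; the missing reason for centre, since the self-rating clause is attached to the baseline adjustment and a fixed effect was available; and an interval sentence that is wrong as written.

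**Conclusion.** The point holds as one of disclosure and technical correctness, and should be fixed. SAP 7.3 describes a data-driven, post hoc analysis whose relation to the 6.3.1 models is not stated. Leaving out centre is conservative and costs about 0 to 9 points of power, depending on a between-centre SD that the documents do not give. The reason for the intervals is wrong for limits based on a standard error and irrelevant to the between-arm effect; no consequence for the estimate itself has been shown. The 6 to 9% illustrates free choice between two analyses and does not estimate this trial's error rate. All simulated figures use the planning distribution with assumed correlations and centre effects, and without the imputation of SAP 6.4. The observed distribution (Figure 1) is not shown.

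**What to change.** In SAP 7.3:
- State that the 6.3.1 mixed model with centre remains primary and is reported first, and that the sensitivity model planned in 6.3.1 is still reported.
- Label the median regression as post hoc, chosen after the outcome was seen by arm, and supportive only.
- Keep centre in it, for example as a fixed effect with resampling within centre, or give the reason for leaving it out.
- Delete the claim that bootstrapped standard errors keep limits below 100. If arm-level medians are shown with bounded limits, use percentile limits and say so.

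The cost is a few sentences and, if centre is kept, one re-run. The real downside is that the median result cannot be the headline, and the mean analysis may be the less powerful one if the lower tail is heavy. With an assumed 10% or 20% of both arms drawn from N(40, 15), power was 53% and 36% for the mixed model against 59% and 45% for the adjusted median. Without such a tail it was 82% against 72% in favour of the mixed model. Which case applies cannot be told without Figure 1.
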